3.2.1.1.3 Duration of response [DoR]

Duration of response will be defined as the time from the date of first documented response (which is subsequently confirmed) until date of documented progression or death in the absence of disease progression (i.e., date of PFS event or censoring – date of first response + 1). The end of response should coincide with the date of progression or death from any cause used for the PFS endpoint. The time of the initial response will be defined as the latest of the dates contributing towards the first visit that was PR or CR that was subsequently confirmed.

If a patient does not progress following a response, then their DoR will use the PFS censoring time.

3.2.1.1.4 Change in tumour size

Change in tumour size at Week 12

Change from baseline in TL's tumour size at 12 weeks and over time will be based on RECIST TLs measurements taken at baseline and at post-baseline assessments. Tumour size is the sum of the longest diameters (or short axis measurements for lymph nodes) of the target lesions. Target lesions are measurable tumour lesions. Baseline for RECIST is defined to be the last evaluable assessment prior to starting treatment.

The percentage change in TL tumour size at post-baseline assessments will be obtained for each patient taking the difference between the sum of the TLs at timepoint and the sum of the TLs at baseline divided by the sum of the TLs at baseline times 100 (ie, $[\text{timepoint} - \text{baseline}]/\text{baseline} \times 100$). Only patients with measurable disease at baseline should be included in summaries of best percentage change in tumour size (measurable disease is as denoted on the CRF by the investigator).

No imputation will be used for summaries of the percentage change in tumour size from baseline by visit, but for summaries of the percentage change at Week 12, imputation will be used.

For patients who have less than or equal to one-third of TLs missing at week 12, assessment data from missing lesions may be scaled up proportionally to the sum of the corresponding lesions at baseline to give an estimated sum of diameters as described in the RECIST section of the protocol and Section 3.2.1.1.1 of this SAP. Whenever TL tumour size data for the visit is available then this should be used in the summary tables and figures.

If after applying these considerations there is still missing TL tumour size measurement data [tsm data] at week 12, the following imputation process for each individual patient where data is missing should be applied:

- a) If there is no observed TLtsm data at week 12, but there is TL tsm data collected at a visit prior to week 12 or the first visit after week 12, use all of the available data up to and including the first visit after week 12 (i.e. baseline and all visits up to and including the first visit after week 12) to fit a linear regression to the individual patient's baseline and follow-up assessment(s). Note that actual day of the measurement rather than planned day should be used in the fitting of this model. This model can then be used to generate an estimated value for TL tsm at week 12

and hence impute a change from baseline at week 12.

- b) If there is no observed TL tsm data at week 12 but there is evidence of progression for the individual prior to the end of the time window used to select week 12 data, where evidence of progression is defined as progression of NTLs, the appearance of new lesions or as determined by an investigator (i.e. investigator's opinion of response recorded on the RECIST CRF is PD at that assessment or study treatment was discontinued for progression in the assessment time window), and there are at least 5 patients with non-missing TL tumour size who have also progressed then impute a change from baseline at week 12 as the median percentage change from patients with non-missing TL tumour size who also have progressed. If the patient has an imputed value from a), use the maximum of this median value or the imputed value in the tumour size analysis. However, if there are less than 5 patients with non-missing tumour size who have also progressed then impute a change from baseline at week 12 as 20%. If the patient has an imputed value from a), use the maximum of 20% or the imputed value in the tumour size analysis.
- c) If there is no evidence of progression for the individual, use the imputed value calculated in a) if data available. If there is no evidence of progression for the individual and no observed TL tsm data is collected at a visit prior to week 12 or the first visit after week 12, assume that the data is missing completely at random. The patient will be excluded from the analysis.
- d) If it is known that the patient has died prior to the end of the time window used to select week 12 data, impute a change from baseline at week 12 as the maximum of the observed or imputed (from step b) percentage change reported in the study for week 12.

Best percentage change in tumour size

The best percentage change in tumour size for each patient is the biggest decrease or the smallest increase in TL tumour size from baseline in the absence of a decrease.

If a patient has no post baseline assessments, then the following imputation rules should be applied:

- a) If there is no observed TL tsm data post progression but there is evidence of progression for the individual during their time on study, where evidence of progression is defined as progression of NTLs, the appearance of new lesions or as determined by an investigator (i.e. investigator's opinion of response recorded on the RECIST CRF is PD at that assessment or study treatment was discontinued for progression in the assessment time window), and there are at least 5 patients with non-missing TL tumour size who have also progressed then impute a best percentage change from baseline as the median best percentage change from patients with non-missing TL tumour size who also have progressed. However, if there are less than 5 patients with non-missing TL tumour size who have also progressed then impute a best percentage change from baseline as 20%.
- b) If there is no evidence of progression, assume that the data is missing completely at random; the patient will be excluded from the analysis.
- c) If it is known that the patient has died, impute a best percentage change from baseline as the minimum (i.e. corresponding to the biggest increase in TL tumour size) best percentage change reported on the study.

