3.2 Outcome variables

3.2.1 Efficacy Outcome Variables

3.2.1.1 Calculation or derivation of tumour response variables

3.2.1.1.1 RECIST visit responses

For all patients, the RECIST tumour response data will be used to determine each patient's visit response according to RECIST version 1.1. It will also be used to determine if and when a patient has progressed in accordance with RECIST and also their best objective response to study treatment.

Baseline radiological tumour assessments are performed as defined in [Section 3.1.1](#). Follow-up assessments should be performed every 6 weeks (± 7 days) until Cycle 7 (i.e., 24 weeks) and then every 8 weeks (± 7 days) (relative to randomisation [patients recruited under CSP v7.0] or the first dose of treatment)[patients recruited prior to CSP v7.0] until objective disease progression as defined by RECIST 1.1 even if a patient discontinues treatment prior to progression (unless they withdraw consent). Any other regions suspected, or with known metastasis at baseline, will be assessed by imaging and recorded at baseline. The same imaging modality and the same assessment should be performed at baseline and at all subsequent assessments. If scans are performed outside of the scheduled visit ± 1 week window interval and the patient has not progressed, every attempt should be made to perform the subsequent scans at their scheduled time points.

From the investigator's review of the imaging scans, the RECIST tumour response data will be used to determine each patient's visit response according to RECIST version 1.1. At each visit, patients will be programmatically assigned a RECIST 1.1 visit response of CR, PR, SD or PD, using the information from TLs, NTLs and new lesions and depending on the status of their disease compared with baseline and previous assessments. If a patient has had a tumour assessment which cannot be evaluated, then the patient will be assigned a visit response of not evaluable [NE] (unless there is evidence of progression in which case the response will be assigned as PD).

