4.2.2.13.1 Target Population Analysis Set

Percentage change from baseline in target lesion tumour size at Week 12 and over time, will be summarised.

Also, the best percentage change in tumour size from baseline over all tumour assessment time points will be summarised using descriptive statistics (n, mean, standard deviation, median, minimum, maximum).

The number and percentage of patients with new lesions by lesion site (e.g., CNS) will be tabulated. Waterfall plots showing the percentage change at Week 12 and the best percentage change from baseline in sum of the diameters of TLs will be produced.

Spider plots showing the percentage change from baseline in tumour size for each patient over time may be produced. These plots depict each patient's percentage change in TL tumour size as a line over time. Imputation will not be used for spider plots.

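### The Week 12 tumour-size imputation has no lower bound, so a deep Week 6 response with no later scan can be imputed as a negative sum of diameters

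*SAP*

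**What the plan says.** SAP 3.2.1.1.4 (Change in tumour size at Week 12) lets up to one-third of missing lesions be scaled up. If the Week 12 size is still missing, four rules follow.

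- **Rule a)** applies when there is a measurement at a visit before Week 12 or at the first visit after it. The instruction is to "use all of the available data up to and including the first visit after week 12" in a linear regression for that patient. On timing it adds: "Note that actual day of the measurement rather than planned day should be used in the fitting of this model". Then: "This model can then be used to generate an estimated value for TL tsm at week 12", from which the change from baseline is taken.
- **Rule b)** covers patients with evidence of progression. They receive the progressors' median or, if fewer than five progressors have data, 20%. The regression value replaces this only if it is worse: "If the patient has an imputed value from a), use the maximum of 20% or the imputed value in the tumour size analysis".
- **Rule c)**: "If there is no evidence of progression for the individual, use the imputed value calculated in a) if data available".
- **Rule d)** gives patients who died the largest Week 12 percentage change in the study.

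The same section says that by-visit summaries are not imputed but the Week 12 summaries are. SAP 4.2.2.13.1 plans a Week 12 summary in the TPAS and a plot of the same values, in a sentence that begins "Waterfall plots showing the percentage change at Week 12 and the best percentage change from baseline in sum of the diameters of TLs will be". Section 4.2.2.13.2 repeats this in the SAF. Only the spider plots are expressly exempted from imputation there.

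**The concern.** Rule a) accepts data from before Week 12 alone. On scan timing, SAP 3.2.1.1.1 says: "Follow-up assessments should be performed every 6 weeks". A patient with neither the Week 12 scan nor the next one therefore normally has just two measurements, baseline and Week 6. The regression is then the exact line through two points, extended well beyond the last observation.

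A sum of diameters cannot be less than zero: Protocol Appendix H 4.2.1 records a vanished lesion as 0 mm. A falling line has no such limit. Rules b) and d) guard only the unfavourable direction, and only for patients who progress or die. Nothing in the section bounds the favourable direction for the remaining patients.

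At stake is whether a planned efficacy display can contain values that are physically impossible. A programmer who followed the SAP would have to publish them or depart from the SAP after seeing the data.

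**Working it through.** The SAP gives no worked figure for this rule, so there is nothing to reproduce. The rule was applied directly.

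**Inputs**

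- Scan timing: every 6 weeks, ±7 days, from randomisation (CSP version 7.0) or first dose (earlier versions), SAP 3.2.1.1.1. Week 6 is taken as Day 43, with a window of Day 36 to Day 50.
- Day numbering: Day 1 follows Day -1, with no Day 0 (SAP 3.1.3). A scan on Day -k is k days before Day 1; Day w is w - 1 days after it.
- Prediction day: the SAP names none. Day 85 (84 days after Day 1) is assumed.
- Baseline scan day: an assumption. Protocol 8.1.1 allows 28 days before treatment, so Days -1, -14 and -28 are used. SAP section 6 says the 28-day window will not be followed, so Day -42 is added.

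**Formula (baseline and Week 6 only)**

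Imputed Week 12 change = Week 6 change × (k + 84) / (k + w - 1)

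The result is below -100% when the Week 6 change is deeper than -100% × (k + w - 1) / (k + 84).

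**Week 6 scan on schedule (w = 43)**

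| Baseline scan | Multiplier | Threshold at Week 6 | A Week 6 change of -60% becomes |
|---|---|---|---|
| Day -1 | 85/43 = 1.98 | -50.6% | -118.6% |
| Day -14 | 98/56 = 1.75 | -57.1% | -105.0% |
| Day -28 | 112/70 = 1.60 | -62.5% | -96.0% |
| Day -42 | 126/84 = 1.50 | -66.7% | -90.0% |

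**Across the ±7-day window**

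- Baseline Day -1: 36/85 = 42.4% (scan on Day 36) to 50/85 = 58.8% (Day 50).
- Baseline Day -28: 63/112 = 56.3% (Day 36) to 77/112 = 68.8% (Day 50).

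For baseline scans within the 28 days, the threshold therefore runs from about -42% to -69%.

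**In millimetres.** With 42 days from baseline to the Week 6 scan and 84 to Week 12, a sum falling from 80 mm to 32 mm is imputed as 80 - 2 × 48 = -16 mm. With a baseline scan on Day -1 it is 80 - 48 × 85/43 = -14.9 mm.

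**Where it does not happen**

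- *Modest partial response.* For a baseline scan on Day -1 and the earliest Week 6 scan (Day 36), the multiplier is 85/36 = 2.36. A change of -40% then becomes -94.4%, still above -100%.
- *A scan after Week 12 exists.* Take scans at 0, 42 and 126 elapsed days and predict at 84. The mean time is 56 and the sum of squares is 56² + 14² + 70² = 8,232. Each scan's weight is 1/3 + 28 × (time - 56)/8,232, which gives 1/7, 2/7 and 4/7. All are positive, so the predicted size cannot be negative. A patient at -60% at both follow-up scans gets -60% × 6/7 = -51.4%; one at -100% at both gets -85.7%.

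**With a floor at 0 mm** (42 and 84 elapsed days, multiplier 2): Week 6 changes of -55%, -60%, -80% and -100% give -100% instead of -110%, -120%, -160% and -200%. Changes of -30%, -40% and -50% are unaffected, at -60%, -80% and -100%.

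**The case against.** The strongest reply is that little depends on this.

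- **Stakes.** SAP Table 3 lists change in tumour size among analyses not in the protocol, and 4.2.2.13 calls it exploratory. No test or decision uses it. ORR, DoR and PFS do not draw on it, by-visit summaries and spider plots are not imputed, and best percentage change has its own rules.
- **Size of the group.** The patient must lack Week 12 data and the next scan, have neither progressed nor died by the end of the Week 12 window, and have shrunk by roughly half or more at Week 6. A reader might infer that anyone who stops for toxicity is caught. The documents do not support that: Protocol 7.1.3 and SAP 3.2.1.1.1 keep scans going after treatment stops. The primary analysis is 6 months after the last randomisation (SAP section 5), so the data cut-off does not create the gap either. Mainly consent withdrawal and missed scans remain.
- **Direction.** A reader might infer that the Week 12 summary as a whole is biased towards benefit. That is not shown. Rules b) and d) push the other way, and the same regression understates a durable response when a post-Week 12 scan exists (-51.4% for a patient steady at -60%).
- **Shape of response.** A reader might also argue that every extrapolated value above -100% is inflated because shrinkage slows after Week 6. The documents contain nothing on that, so it is an assumption.

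All of this stands and limits the point. None of it supplies the missing floor.

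**Conclusion.** The point holds as a minor defect. Rule a), applied through rule c), can return a negative sum of diameters for a patient with only baseline and Week 6 data, no Week 12 or next scan, and no progression or death by the end of the Week 12 window. With an on-schedule Week 6 scan this begins at shrinkage of about 51% to 63% for baseline scans between Day -1 and Day -28. Scan windows widen the range to about 42% to 69%. These figures rest on the assumed baseline days and on Day 85 as the prediction day; a baseline scan before Day -28 raises the threshold.

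The consequence is confined to the Week 12 summary and waterfall plot in the TPAS and SAF. The number of patients cannot be derived from the documents and is probably small. It would be wrong to conclude that responders in general receive impossible values, or that any primary or secondary endpoint is affected.

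**What to change.** Add one sentence to rule a) of SAP 3.2.1.1.4: any predicted sum of diameters below 0 mm is set to 0 mm, so that the imputed change is never lower than -100%. This removes every impossible value and leaves other predictions as they are.

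Marking imputed bars on the Week 12 waterfall plot is a useful option. The sponsor could also restrict the regression to interpolation and carry the last observed change forward otherwise. That is a choice between two unverified assumptions, not a required correction.

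The cost is one line of SAP text and one of code. Mean Week 12 shrinkage may become slightly less favourable. No endpoint definition, sample size or test changes.

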3.2.1.1.5 Progression Free Survival [PFS]

PFS is defined as the time from first dose randomisation (patients recruited under CSP version 7.0) or start of treatment (patients recruited prior to CSP version 7.0) until the date of objective disease progression or death (by any cause in the absence of progression) regardless of whether the patient withdraws from study therapy or receives another anti-cancer therapy prior to progression (i.e. date of PFS event or censoring – date of first dose + 1). Patients who have not progressed or died at the time of analysis will be censored at the time of the latest date of assessment from their last evaluable RECIST assessment. However, if the patient progresses or dies after 2 or more missed visits, the patient will be censored at the time of the latest evaluable RECIST 1.1 assessment prior to the two missed visits.

If the two missed visits are immediately after the baseline scan then the definition of two missed visits should be calculated as 2*(the protocolled time between scans) + the protocol allowed visit window (since there is no need to account for an early initial visit in this case), otherwise this should be calculated as 2*(the protocolled time between scans + the protocol allowed visit window). Given the scheduled visit assessment scheme (i.e. six-weekly for the first 24 weeks then eight-weekly thereafter) the definition of 2 missed visits will change as follows:

Last evaluable RECIST assessment before event	Length of time of 2 missed visits
Baseline	2 x 6 weeks + 1 week for late assessment = 13 weeks
RECIST visit 1	2 x (6 weeks + 1 week) = 14 weeks
RECIST visit 2	2 x (6 weeks + 1 week) = 14 weeks
RECIST visit 3	(6 weeks + 1 week) + (8 weeks + 1 week) = 16 weeks
RECIST visit 4	2 x (8 weeks + 1 week) = 18 weeks
RECIST visit 5 etc	2 x (8 weeks + 1 week) = 18 weeks

If the patient has no evaluable visits or does not have baseline data, they will be censored at Day 1 unless they die within 2 visits of baseline (12 weeks plus 1 week allowing for a late assessment within the visit window).

The PFS time will always be derived based on scan/assessment dates, not visit dates.

RECIST assessments/scans contributing towards a particular visit may be performed on different dates. The following rules will be applied:

- For investigational assessments, the date of progression will be determined based on the **earliest** of the dates of the component that triggered the progression
- When censoring a patient for PFS the patient will be censored at the **latest** of the dates contributing to a particular overall visit assessment

Note: for TLs only, the latest scan date is recorded out of all scans performed at that assessment for the TLs and similarly for NTLs only the latest scan date is recorded out of all scans performed at that assessment for the NTLs.

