9.4.3.2 Analysis of the secondary endpoints

Analyses for the efficacy secondary endpoints will be summarised using the TPAS, CAS, and SAF datasets (see Section 9.3 for analysis set definitions).

Objective response rate

To describe the difference in the efficacy of savolitinib (300 mg bid) in combination with osimertinib and savolitinib (300 mg bid) in combination with placebo in patients with EGFRm+, MET amplified/overexpressed (FISH10+ and/or IHC90+), locally advanced or metastatic NSCLC who have progressed following treatment with 1L osimertinib therapy under CSP version 7.0, ORR with 95% confidence intervals will be constructed in the CAS for:

- Osimertinib + savolitinib (300 mg bid)
- Placebo to osimertinib + savolitinib (300 mg bid)

Additional details for the analysis of ORR on other dosing regimen/lines of therapy/biomarker population will be specified in the SAP.

Duration of response

The DoR will be defined as the time from the date of first documented response until date of documented progression or death in the absence of disease progression (ie, date of PFS event or censoring—date of first response+1). The end of response should coincide with the date of progression or death from any cause used for the PFS endpoint. The time of the initial response will be defined as the latest of the dates contributing towards the first visit response of CR or PR.

If a patient does not progress following a response, then their DoR will use the respective PFS censoring time.

If there are sufficient numbers of responders, and sufficient numbers of responses that have progressed by the point of the analysis, Kaplan-Meier plots of DoR in the responding patients will be produced and appropriate descriptive summary statistics will be presented (n, number of responses that have progressed, median, quartile, minimum and maximum DoR).

Progression-free survival

PFS is defined as the time from randomisation (patients recruited under CSP version 7.0) or start of treatment (patients recruited prior to CSP version 7.0) until the date of objective disease progression or death (by any cause in the absence of progression) regardless of whether the patient withdraws from therapy or receives another anti-cancer therapy prior to progression. Patients who have not progressed or died at the time of analysis will be censored at the time of the latest date of assessment from their last evaluable RECIST assessment.

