However, if the patient progresses or dies after 2 or more missed visits, the patient will be censored at the time of the latest evaluable RECIST assessment. If the patient has no evaluable visits or does not have baseline data, they will be censored at Day 1 unless they die within 2 visits of baseline: in such a case, the death date will be used as the event date.

The PFS time will always be derived based on scan/assessment dates, not visit dates.

RECIST assessments/scans contributing towards a particular visit may be performed on different dates. The following rules will be applied:

- Date of progression will be determined based on the earliest of the dates of the component that triggered the progression.
- When censoring a patient for PFS, the patient will be censored at the latest of the dates contributing to a particular overall visit assessment.

Summaries of PFS (n, events, medians, quartiles, proportion progression free at **CCI** months and corresponding 95% CIs) and Kaplan-Meier plots will be provided by treatment group.

Progression-free survival based on investigator assessment will be analysed using a stratified log-rank test adjusting for the stratification used in randomisation for the generation of the p-value. The effect of treatment will be estimated by the HR together with its corresponding 95% CI for the CAS. An HR less than 1 will favour savolitinib plus osimertinib. The HR and its CI will be estimated from a Cox Proportional Hazards model (with ties = Efron and baseline stratification) and the CI calculated using a profile likelihood approach. If there are insufficient events per strata, a log-rank test will be used to analyse PFS instead of a stratified log-rank test.

Overall survival

OS is defined as the time from randomisation (patients recruited under CSP version 7.0) or the start of treatment (patients recruited prior to CSP version 7.0) until death due to any cause. Any patient not known to have died at the time of analysis will be censored based on the last recorded date on which the patient was known to be alive.

Note: Patients will be contacted for survival follow-up every 12 weeks. Patients should be contacted in the week after data cut-off for each analysis to establish survival status. The impact of cross over on OS may need to be assessed depending on the number of patients crossing over to savolitinib plus osimertinib. Further details will be provided in the SAP.

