3.1.3 Time Windows

The date of first dose of study treatment will be considered Day 1, and the day before the first dose of study treatment will be Day -1. Relative days will be calculated as follows:

For days on or after the first dose of study treatment:

Date of assessment – Date of first dose of study treatment +1.

For days before the first dose of study treatment:

Date of assessment – Date of first dose of study treatment.

For analyses of efficacy variables for patients enrolled under CSP version 7.0, the date of randomisation will be considered Day 1, and the day before date of randomisation will be Day -1. Relative days will be calculated as follows:

For days on or after the randomisation date:

Date of assessment – Date of randomisation +1.

For days before the randomisation date:

Date of assessment – Date of randomisation.

For non-efficacy analysis, the study day is still relative to first dosing date of study treatment.

Study days will only be calculated for complete assessment dates (i.e. partial dates will have missing study day).

The time from last dose of treatment to death will be derived for complete dates as follows:

Date of death – Date of last dose of treatment

For the purpose of the statistical analysis and if not otherwise specified, all the variables (primary, secondary and exploratory variables) will be assigned to the visit/assessment timepoint in which they were collected depending on the following analysis time windows in Table 5. Where appropriate, the window for assessment days following baseline will be constructed in such a way that the upper limit of the interval falls halfway between the two timepoints.

Table 5 Time Windows

Cycle	Week	Study Day	Cycle Day	Study Day window for weekly assessments	Cycle Day window for weekly assessments	Cycle Day window for Cycle Day 1 assessments (from Cycle 2 and onwards)	Study Day window for assessments scheduled every 4 weeks [b]	Study Day window for assessments scheduled every 6 weeks	Cycle Day window for liver function tests (ALT, AST, ALP and total bilirubin)	Cycle Day window for safety laboratory assessments (other than liver function tests)
		-1	-1	-28 to -1	-1	-1	-1	-1	-1	-1
1	1	1 [a]	C1D1	1	C1D1	C1D1	1	1	C1D1	C1D1
1	2	8	C1D8	2-11	C1D2- C1D11	C1D2- C1D11	2-42	2-63	C1D8	C1D8
1	3	15	C1D15	12-18	C1D12- C1D18	C1D12- C1D18			C1D15	C1D15
1	4	22	C1D22	19-25	C1D19- C1D25	C1D19- C1D25			C1D22	C1D22
2	5	29	C2D1	26-32	C1D26- C2D4	C1D26-			C2D1	C2D1 [d]

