3.2.1.1.6 Overall survival [OS]

Overall survival is defined as the time from randomisation (patients recruited under CSP version 7.0) or the start of treatment (patients recruited prior to CSP version 7.0) until death due to any cause (i.e. date of death or censoring – date of first dose + 1). Any patient not known to have died at the time of analysis will be censored based on the last recorded date on which the patient was known to be alive.

Patients will be contacted for survival follow-up every 12 weeks. In addition to survival data, information regarding any subsequent anti-cancer treatment will also be collected. The impact of cross over on OS may need to be assessed.

Patients should be contacted in the week after data cut-off [DCO] for each analysis to establish survival status, and if patients are confirmed to be alive or if the death date is after the DCO date these patients will be censored at the date of DCO. The status of ongoing, withdrawn (from the study) and “lost to follow-up” at the time of the final OS analysis should be obtained by the site personnel by checking the patient’s notes, hospital records, contacting the patient’s general practitioner and checking publicly-available death registries. In the event that the patient has actively withdrawn consent to the processing of their personal data, the vital status of the patient can be obtained by site personnel from publicly available resources where it is possible to do so under applicable local laws.

It may be necessary to use all relevant eCRF fields to determine the last recorded date on which the patient was known to be alive for those patients still on treatment. The last date for each individual patient is defined as the latest among the following dates recorded on the case report forms [CRFs]:

- AE start and stop dates
- Admission and discharge dates of hospitalization
- Study treatment date
- End of treatment date
- Laboratory test dates
- Date of vital signs
- Disease assessment dates on RECIST CRF
- Start and stop dates of alternative subsequent anticancer treatment (including radiotherapy)
- Date last known alive on survival status CRF
- End of study date

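### SAP formulas for PFS and OS time version 7.0 patients from first dose, not randomisation, and its treated-patient ORR base conflicts with the all-randomised CAS

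*SAP*

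**What the plan says.** **Time origin.** Protocol 9.4.3.2 sets it for both endpoints: "PFS is defined as the time from randomisation (patients recruited under CSP version 7.0) or start of treatment" for earlier patients, and "OS is defined as the time from randomisation (patients recruited under CSP version 7.0) or the start of treatment" likewise. SAP 3.1.3 agrees: "For analyses of efficacy variables for patients enrolled under CSP version 7.0, the date of randomisation will be considered Day 1".

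SAP 3.2.1.1.5 opens with "PFS is defined as the time from first dose randomisation (patients recruited under CSP version 7.0", which names two origins at once. Its bracketed calculation then reads "date of PFS event or censoring – date of first dose + 1", with no exception for version 7.0. A patient with no evaluable visit or no baseline is handled as follows: "they will be censored at Day 1 unless they die within 2 visits of baseline".

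SAP 3.2.1.1.6 begins "Overall survival is defined as the time from randomisation (patients recruited under CSP version 7.0) or the start of treatment", but its formula is "date of death or censoring – date of first dose + 1".

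**ORR base.** SAP 3.2.1.1.2 bases ORR on treated patients, or on treated subsets defined by MET test. SAP 4.2.2.2.1 builds the two-arm ORR in the Contribution of Components Analysis Set (CAS). SAP 2.2, Table 2, defines the CAS as everyone randomised under version 7.0, by randomised arm, whatever they went on to take. SAP 4.1 makes the analysis set total the default denominator, but only where nothing else is stated. Protocol 9.4.3.1 gives a third base for the primary endpoints: dosed patients who had measurable disease at baseline.

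SAP section 6, which lists departures from the protocol, mentions neither the time origin nor the denominator.

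**The concern.** The two brackets are the only explicit time calculations for PFS and OS, so they are what a programmer is likely to code. For version 7.0 patients they contradict the protocol, the SAP's Day 1 rule and, for OS, the sentence they sit in. Two programmers could derive different times and each cite the SAP.

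Three things follow from the literal reading:

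- A randomised but undosed patient has no first-dose date and so no PFS time. The SAP foresees such patients as important deviation 5.07 in Table 4. They belong to the CAS but could not enter its stratified log-rank test or Cox model (SAP 4.2.2.4.3), and the treated-patient base removes them from the CAS ORR.
- A patient censored at Day 1, which SAP 3.1.3 makes the randomisation date, but dosed later gets a zero or negative time.
- Every other version 7.0 PFS and OS time is shortened by the gap from randomisation to first dose.

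The CAS is the study's only blinded comparison of the combination with savolitinib plus placebo. Excluding patients after randomisation weakens that comparison.

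**Working it through.** The documents give no gap, no count of undosed patients and no unredacted CAS size, so there is no planned figure to reproduce. What follows is exact date arithmetic, then illustrations under stated assumptions.

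**1. Effect on each time.** Let R be the randomisation date, D = R + g the first-dose date and E the event or censoring date.

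- From randomisation: E − R + 1.
- As the formula is written: E − D + 1 = (E − R + 1) − g.

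Each time is short by g days. With 365.25/12 days per month, g = 3 gives 0.10 months and g = 7 gives 0.23 months.

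**2. Day 1 censoring.** Put E = R. The written formula gives R − (R + g) + 1 = 1 − g.

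| g (days) | From randomisation | As written |
|---|---|---|
| 0 | 1 | 1 |
| 1 | 1 | 0 |
| 3 | 1 | −2 |
| 7 | 1 | −6 |

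**3. Hazard ratio in the CAS.** Assumptions:

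- 60 combination and 30 monotherapy patients. The 2:1 ratio is in the documents; the sizes are not.
- Exponential PFS with medians of 8 and 3 months, and uniform censoring between 6 and 18 months.
- Unstratified Cox model with Efron ties, 1000 runs per scenario.
- The literal rule subtracts the gap and drops undosed patients and non-positive times.
- Where patients are undosed, they have events at days 5 to 42 and the gap for the others is 0 to 3 days.

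| Scenario | HR from randomisation | HR as written | Ratio |
|---|---|---|---|
| None undosed, gap 0–3 days | 0.372 | 0.372 | 1.000 |
| None undosed, gap 0–7 days | 0.372 | 0.371 | 0.999 |
| 1 monotherapy undosed | 0.357 | 0.366 | 1.026 |
| 2 monotherapy undosed | 0.352 | 0.370 | 1.052 |
| 1 combination undosed | 0.380 | 0.367 | 0.966 |
| 2 combination undosed | 0.395 | 0.369 | 0.932 |
| 2 combination + 1 monotherapy | 0.382 | 0.365 | 0.956 |
| 4 combination + 2 monotherapy | 0.405 | 0.372 | 0.918 |

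The last digit of a ratio can differ from that of the printed HRs because of rounding. Widening the gap to 0–7 days barely changes the ratios: 1.052 (2 monotherapy), 0.955 (2 + 1) and 0.917 (4 + 2). If the undosed patients are instead censored at Day 1, the ratio is 0.999 to 1.000.

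In the 2 + 1 and 4 + 2 cases the undosed fraction is equal in both arms (2/60 = 1/30 = 3.3%; 4/60 = 2/30 = 6.7%), and the literal rule still favours the combination.

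**4. ORR in the CAS.** Take the 55% assumed for the combination in protocol 9.2, an assumed 20% for monotherapy (that value is redacted), and 4 + 2 undosed non-responders. Intervals are 95% Clopper-Pearson.

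| Arm | All randomised | Treated only |
|---|---|---|
| Combination | 33/60 = 55.0% (41.6–67.9) | 33/56 = 58.9% (45.0–71.9) |
| Monotherapy | 6/30 = 20.0% (7.7–38.6) | 6/28 = 21.4% (8.3–41.0) |
| Difference | 35.0 points | 37.5 points |

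**5. Reach.** The Target Population Analysis Set (TPAS) and Safety Analysis Set (SAF) both require at least one dose, so a treated-patient base agrees with them. The OS formula touches mainly dosed version 7.0 patients in the TPAS. SAP 4.2.2.5 plans OS for TPAS and SAF, and the CAS appears for OS only in the Appendix A subgroup table.

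**The case against.** The best defence is that the brackets are leftover text. The surrounding sentences, SAP 3.1.3, the scan schedule in SAP 3.2.1.1.1 and the protocol all point to randomisation, so the intent is clear. No passage tells anyone to drop undosed patients. The CAS is defined as all randomised, and a missing first-dose date only makes the bracket unusable. SAP 3.2.1.1.2 is a general definition that does not name the CAS, so the specific CAS section and the default in SAP 4.1 could be read as governing.

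On size, every non-trivial hazard ratio shift assumes that all undosed patients have early events. Eligibility requires performance status 0 or 1 and a life expectancy of at least 12 weeks. The first scheduled scan is at week 6 ± 7 days, so most such events would have to be deaths or unscheduled progressions. The simulation is also unstratified, unlike the planned analysis. Finally, the protocol's measurable-disease denominator concerns the primary endpoints, not the CAS.

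Much of this stands as to intent and size. The time-origin effect is negligible unless undosed patients have early events, and the larger ratios are illustrations, not forecasts. It does not remove the contradiction. The endpoint definition is more specific than the Day 1 rule, and the SAP 4.1 default yields where another base is stated, which SAP 3.2.1.1.2 does. Measurable disease is an entry criterion, so that denominator difference should matter little in practice, but it is still undeclared.

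**Conclusion.** The concern holds. As written, the SAP's PFS and OS calculations give the wrong time origin for version 7.0 patients, and its stated ORR base does not match the set in which the randomised ORR is reported.

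The consequence is limited. It is nil if every patient is dosed on the day of randomisation. A gap of up to 7 days alone leaves the hazard ratio essentially unchanged. A material change needs randomised, undosed patients. With early events in a few of them, in the assumed 60:30 CAS, the hazard ratio moves by a factor between 0.918 and 1.052, in a direction that depends on arm. The assumed 4 + 2 case adds 2.5 points to the ORR difference. The CAS objective is descriptive, with ORR as its endpoint, and the two primary ORR analyses are essentially unaffected. It should still be corrected before analysis, because otherwise the rule could be chosen with the results in view.

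**What to change.** - **SAP 3.2.1.1.5 and 3.2.1.1.6:** for version 7.0 patients, compute event or censoring date minus randomisation date plus 1. Keep first dose as the origin only for earlier patients. Remove the stray mention of first dose from the opening PFS sentence.
- **SAP 3.2.1.1.2:** state one denominator per set. For the CAS, use all randomised patients, with undosed patients counted as non-responders. For TPAS and SAF, use all patients in the set.
- **SAP section 6:** declare the difference from the protocol 9.4.3.1 denominator.
- **Optional, for consistency:** time the minimum interval for stable disease in SAP 3.2.1.1.2 from randomisation for version 7.0 patients. This can change best-response categories only at the window edge and cannot change ORR.

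The cost is SAP wording and a few lines of derivation code, with no new data. The CAS ORR may come out slightly lower.
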